## SYNOPSIS OF PROTOCOL NUMBER ML 27860

TITLE	Phase IIIb, open-label study of erlotinib (Tarceva ® ) treatment in patients with locally advanced or metastatic non-small cell lung cancer who present activating mutations in the tyrosine kinase domain of the epidermal growth factor receptor.		
SPONSOR	Roche d.o.o	CLINICAL PHASE	IIIb
INDICATION	Locally advanced (stage IIIB with supraclavicular lymph node metastases or malignant pleural or pericardial effusion), or metastatic (stage IV) non-small cell lung cancer (NSCLC).		
OBJECTIVES	
Primary:            Efficacy of erlotinib (TarcevaTM, 150 mg) on progression-free survival (PFS) in patients with non-small-cell lung cancer (NSCLC) in locally advanced or metastatic stages (stage IIIB and stage IV) who have not received previous chemotherapy for their disease and who present activating mutations in the tyrosine kinase (TK) domain of the epidermal growth factor receptor (EGFR).
 
Secondary:
 
 
• Response rate,
 
• Safety profile,
 
• To assess the incidence of EGFR mutations in NSCLC patients tested in Serbia.
 
• Quality of Life (QoL)
 
		
TRIAL DESIGN	Open-label, multi-center Phase IIIb study		
NUMBER OF SUBJECTS	300 patients		
TARGET POPULATION	Patients with histologically or cytologically confirmed locally advanced or metastatic (stage IIIB/IV) NSCLC who have not received previous chemotherapy for their disease and who present activating mutations in the TK domain of the EGFR.		
INCLUSION CRITERIA	
 
1. Patients able and willing to give written informed consent. Consent must be obtained prior to any study-specific procedure.
 
2. Histologically or cytologically documented inoperable, locally advanced (stage IIIB with supraclavicular lymph node metastases or malignant pleural or pericardial effusion) or metastatic (stage IV) NSCLC disease who present activating mutations (exon 19 deletions or exon 21 substitution L858R) in the tyrosine kinase domain of EGFR.
 
3. Measurable disease must be characterized according to the Response Evaluation Criteria in Solid Tumors (RECIST) criteria.
 
4. Male or female patients aged <math>\geq</math> 18 years.
 
5. Eastern Cooperative Oncology Group (ECOG) performance
 
		

- 
- status 0-2.
6. Life expectancy  $\geq$  12 weeks.
  7. Adequate hematological function: Absolute neutrophil count (ANC)  $\geq 1.5 \times 10^9/L$ , and Platelet count  $\geq 100 \times 10^9/L$ , and Hemoglobin  $\geq 9 \text{ g/dL}$  (may be transfused to maintain or exceed this level).
  8. Adequate liver function: Total bilirubin  $< 1.5 \times$  upper limit of normal (ULN), and aspartate aminotransferase (ASAT), alanine aminotransferase (ALAT)  $< 2.5 \times$  ULN in patients without liver metastases;  $< 5 \times$  ULN in patients with liver metastases.
  9. Adequate renal function: Serum creatinine  $\leq 1.25 \times$  ULN, Creatinine clearance  $\geq 60 \text{ ml/min}$ .
  10. Able to comply with the required protocol and follow-up procedures, and able to receive oral medications.
  11. Female patients must be postmenopausal (24 months of amenorrhea), surgically sterile or they must agree to use a physical method of contraception. Male patients must be surgically sterile or agree to use a barrier method of contraception. Women with an intact uterus (unless amenorrhoeic for the last 24 months) must have a negative pregnancy test (urine or serum) within 3 days prior to enrolment into the study. Male and female patients must use effective contraception during the study and for a period of 60 days following the last administration of erlotinib. Acceptable methods of contraception include an established hormonal therapy or intrauterine device for females, and the use of a barrier contraceptive (i.e. diaphragm or condoms) with spermicide.
  12. Patients with asymptomatic and stable cerebral metastases receiving medical treatment will be eligible for the study. Those patients may have received radiation therapy for their cerebral metastases before the initiation of systemic treatment for non-small-cell lung cancer also will be eligible.

---

#### EXCLUSION CRITERIA

1. Previous treatment with chemotherapy or therapy against EGFR, either with antibody or small molecule (tyrosine kinase inhibitor) for metastatic disease. The administration of neoadjuvant or adjuvant therapy is allowed as long as it has finalized  $\geq 6$  months before entering the study. Patients can have received radiotherapy as long as the irradiated lesion is not the only target lesion for evaluating response and as long as radiotherapy has been completed before initiating the study treatment (a 2-week period is recommended).
2. Treatment with an investigational drug agent during the 3 weeks before enrollment in the study.
3. History of another neoplasm other than carcinoma in situ of the uterine cervix, basal cell skin carcinoma treated adequately, or

---

prostate carcinoma with a good prognosis (Gleason  $\leq$  6) treated radically. History of another neoplasm treated curatively and without evidence of disease in the last 5 years.

4. Patients with symptomatic cerebral metastases.
5. Known hypersensitivity to erlotinib or any of its excipients.
6. Any significant ophthalmologic abnormality, especially severe dry eye syndrome, keratoconjunctivitis sicca, Sjögren's syndrome, severe exposure keratitis or any other disorder likely to increase the risk of corneal epithelial lesions. The use of contact lenses is not recommended during the study. The decision to continue to wear contact lenses should be discussed with the patient's treating oncologist and the ophthalmologist.
7. Coumarins (CoumadinTM; warfarin) use. If the patient requires anti-coagulation therapy, the use of low molecular weight heparin instead of coumarins is recommended where clinically possible.
8. Unstable systemic disease (including active infection, uncontrolled hypertension, unstable angina, congestive heart failure, myocardial infarction within the previous year, serious cardiac arrhythmia requiring medication, hepatic, renal, or metabolic disease).
9. Evidence of any other disease, neurological or metabolic dysfunction, physical examination or laboratory finding giving reasonable suspicion of a disease or condition that contraindicates the use of an investigational drug or puts the patient at high risk for treatment-related complications.
10. Positive urine or serum pregnancy test in women of childbearing potential. Patients (male or female) with reproductive potential not willing to use effective method of contraception. Female patients should not be pregnant or breast-feeding. Oral or injectable contraceptive agents cannot be the sole method of contraception.
11. Patients with pre-existing parenchymal lung disease such as pulmonary fibrosis, lymphangiosis carcinomatosis.
12. Patients with known infection with HIV, HBV, HCV. Testing is not required in the absence of clinical signs and symptoms suggestive of these conditions.
13. Patients assessed by the investigator to be unable or unwilling to comply with the requirements of the protocol.
14. Incapacity to take oral medication or previous surgical procedures that affect absorption and imply the need for intravenous or parenteral feeding.

---

LENGTH OF STUDY	This study is event-driven, with a recruitment period of approximately 24 months. Patients are to be treated until disease progression, unacceptable toxicity, death or patient request for discontinuation.
END OF STUDY	The study will end when the last patient has stopped erlotinib therapy

---

	and completed their last visit. For all patients who have discontinued study drug treatment and are alive, information on survival will be collected.
INVESTIGATIONAL MEDICAL PRODUCT(S) DOSE/ ROUTE/ REGIMEN ASSESSMENTS OF:	Patients will be dosed daily with 150 mg erlotinib taken orally until disease progression or unacceptable toxicity. Dose reduction will be allowed according to protocol (Section 6.1.1.)
EFFICACY	
Primary endpoint:
 
 
• PFS, defined as the time from the first dose of erlotinib to the date of first occurrence of disease progression or death.
 
 
Secondary endpoints:
 
 
• Response rate and disease control rate based on best response measured according to RECIST criteria.
 

SAFETY	All adverse events (AEs) will be assessed using the National Cancer Institute Common Terminology Criteria for AEs (NCI CTC-AE) version 4.0. The incidence of serious adverse events (SAEs) and non-SAEs related to erlotinib therapy will be determined. Additional information about AEs of special interest (serious and non-serious) such as rash and diarrhea will be collected.
INCIDENCE OF EGFR MUTATION RATES IN SERBIA	
If patients are deemed eligible to participate in the study by the investigator, EGFR mutation analysis will be performed at [REDACTED] [REDACTED] for oncology and radiology of Serbia or at Private Laboratory [REDACTED].
 
Patients whose tumors present activating mutations (exon 19 deletions or exon 21 substitution L858R) in the TK domain of EGFR gene are eligible to be enrolled in therapeutic phase of the study.
 
The incidence of EGFR mutations among NSCLC patients tested in Serbia will be assessed.

QUALITY OF LIFE	
Quality of life will be measured using the FACT-L method. This is a validated measure of quality of life.
 
FACT-L Quality of Life questionnaires will be administered to patients prior to therapy, at each visit and at the final study visit, 4 weeks after patients progressed.

---

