## PART I: STUDY DESIGN AND CONDUCT

### 1. BACKGROUND AND RATIONALE

#### 1.1 Background

##### 1.1.1 Non-small cell lung cancer

Lung cancer is the most common cause of cancer death worldwide, accounting for up to 18% of cancer-related deaths (Parkin et al., 2005). Non-small cell lung cancers (NSCLC) comprise 80% of reported lung cancer cases (Cartman et al., 2002). Indeed, the majority of new cases of lung cancer are advanced NSCLC (Haura, 2001). Due to late diagnosis, only a small proportion of NSCLC cases are operable as over 60% of patients present with advanced stages of the disease (Makitaro et al., 2002). In comparison with other solid tumors, the objective response and overall survival (OS) rates in patients with advanced NSCLC are low: five-year survival rates for stage IIIB inoperable disease are less than 10%, decreasing to less than 2% in disease stage IV (Ginsberg et al., 2001).

For this population of patients in whom treatment is mainly palliative, the main goal is to achieve symptom control and prolong overall survival (Vansteenkiste, 2007). Standard of care for patients with locally advanced or metastatic NSCLC is platinum-based doublet chemotherapy (Pfister et al., 2004). Doublet chemotherapy has been found to be superior to single-agent chemotherapy (Delbaldo et al., 2004), with cisplatin-based therapy the current reference treatment for patients with advanced NSCLC. However, no doublet combination has been proven to be clinically superior to the others (Greco et al., 2002; Scagliotti et al., 2002; Schiller et al., 2002; Smit et al., 2003). Current data suggest that chemotherapy has reached a therapeutic plateau, conferring no improvements in survival despite the availability of new combinations of cytotoxic agents (Helbakkmo et al., 2007; Schiller et al., 2002). Overall, the survival outcomes for NSCLC patients remain poor, with a one-year survival rate of only 35% (Ettinger, 2002).

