### **3.1 Overview of Study Design**

This is a open-label, multi-center Phase IIIb study of erlotinib treatment in patients with locally advanced or metastatic non-small cell lung cancer who present activating mutations in the tyrosine kinase domain of the epidermal growth factor receptor.

The first part of the study is the diagnostic phase which will test patients with advanced or metastatic NSCLC for EGFR mutations. Patients who do not have an EGFR mutation will be excluded from the trial. Patients found to have a tumour with EGFR mutations will then be offered treatment in the treatment phase of the study. The treatment phase is a single arm, open label study using erlotinib as first-line therapy. All enrolled patients into the treatment phase will receive erlotinib 150 mg/day until event. Erlotinib dose will be reduced for toxicities as detailed in Section 6.1.1. Event is defined as progression of disease, death, unacceptable toxicity or withdrawal of consent.

Summary of the study design is shown in Figure 1.

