## **5.3 Clinical Assessments and Procedures**

Clinical and safety assessments will be performed at Screening and Baseline and on Day 1 of every 6th week until PD, death, or unacceptable toxicity, as indicated in the Schedule of Assessments.

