**Table 2 Guidelines for management of erlotinib-related toxic effects:**

Toxicity	Grade	Guideline for management	Dose modification of erlotinib*
Keratitis	2	Interrupt the treatment. Ophthalmologic assessment.	Hold until recovery, and then restart at reduced dose. Continue regular ophthalmological assessments while

			on treatment.
	$\geq 3$	Discontinue treatment and seek ophthalmological advice	
Diarrhea	1	No intervention	None
	2	Loperamide (4 mg at first onset, followed by 2 mg every 2-4 hours until diarrhea-free for 12 hours)	None**
	3		Hold until recovery to $\leq$ grade 1, and then restart at reduced dose.
	4	Discontinue treatment	
Rash	1	No intervention	None
	2	Any of the following: minocycline a , topical tetracycline or clindamycin, topical silver sulfadiazine, diphenhydramine, oral prednisone (short course)	None**
	3		Hold until recovery to $\leq$ grade 2, and then restart the dose.
	4	Discontinue treatment	
Other toxicity	$\geq 2$ prolonged clinically significant toxicity	Treatment as appropriate	Hold until recovery to $\leq$ grade 1, and then restart at reduced dose.

\* If no recovery after 14 days of holding drug, patients should be discontinued from the study

\*\* If dose has been previously held for grade 2 rash or diarrhea, and grade 2 symptoms recur, or if the patient finds the symptoms unacceptable, hold dose until recovery to  $\leq$  grade 1 and then reduce the dose.

a Recommended dose: 200 mg p.o. b.i.d. (loading dose), followed by 100 mg p.o. b.i.d. for 7-10 days.

If symptoms of the same degree reoccur after re-initiating the treatment at reduced dose a further dose reduction will be required or patients should be discontinued from the study.

Dosing may be interrupted for a maximum of 14 days if clinically indicated and if the toxicity is not controlled by optimal supportive medication. Patients who require an interruption in dosing of  $> 14$  days will discontinue treatment and be taken off study.

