### **8.1 Primary and Secondary Study Variables**

#### **8.1.1 Primary Variable**

The primary efficacy variable is progression free survival (PFS). The time to progression is defined as the time from start of treatment to the date of the first documented progression (according to RECIST criteria) or the date of death for any reason in the absence of PD. Patients who have not died or progressed at the time of the final analysis will be censored at the date of last contact.

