#### **8.1.2 Secondary Variables**

The secondary efficacy variables are the following:

- Response and disease control rates: measured according to RECIST criteria. A patient is defined as a responder if they sustain a complete response (CR) or partial response (PR) for at least 4 weeks during treatment (confirmed response). Disease control is defined as response – as defined above – or stable disease (SD) for at least 6 weeks.
- Incidence of EGFR mutations will be calculated based on evaluable biopsy samples obtained from patients entered into the diagnostic phase of the study.
- Safety of the treatment will be evaluated in the safety population by: adverse events, laboratory tests, vital signs, performance status

- A mean Quality of Life score will be calculated for the QoL tool (FACT-L) at each timepoint for all non-progressing patients. Changes from baseline in patients' QoL score will be summarised for each time point during the study.

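### The synopsis promises survival information after erlotinib is stopped, but the body takes some patients off study and schedules no later contact, so deaths that count as PFS events can be missed

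*Combined protocol and SAP*

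**What the plan says.** The End of Study entry in the synopsis makes the commitment: "For all patients who have discontinued study drug treatment and are alive, information on survival will be collected". It gives no interval, duration or method.

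The body points the other way in several places:

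- Section 6.1.1, closing text: patients needing an interruption of more than 14 "days will discontinue treatment and be taken off study". The Table 2 footnote adds: "If no recovery after 14 days of holding drug, patients should be discontinued from the study".
- Section 3.1: "Event is defined as progression of disease, death, unacceptable toxicity or withdrawal of consent". Toxicity and withdrawal are thus events for the purpose of ending treatment, although neither is a PFS event.
- Section 5.3: clinical and safety assessments run "until PD, death, or unacceptable toxicity, as indicated in the Schedule of Assessments".
- Section 3.1.3 repeats the synopsis definition of study end but not the survival sentence.
- The Schedule of Assessments stops at the final visit or withdrawal column. It has no survival row.

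On the analysis side, Section 8.1.1 makes the PFS event the first documented progression or "the date of death for any reason in the absence of PD". Patients with neither are censored at last contact. The list in Section 8.1.2 that opens "The secondary efficacy variables are the following" contains no survival variable, and Section 8.2 applies Kaplan-Meier methods to PFS only.

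**The concern.** A patient who stops erlotinib for toxicity without progression is still at risk of the primary endpoint. A site that works from Section 6.1.1 and the schedule would close that patient's follow-up, and a later death might never reach the database. The patient would be censored near the date of stopping.

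Intolerance may be related to prognosis, so this censoring cannot be assumed to be non-informative. A site that works from the synopsis would keep collecting vital status, and its patients would be censored later under the last-contact rule. The same clinical course could thus give different PFS records at different sites. At stake is a possible bias in the Kaplan-Meier estimate of PFS, the trial's primary efficacy result.

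**Working it through.** **Planning figure.** The plan states no PFS or survival event count or power. Its only sample-size figure is the 3.5% precision for a 10% mutation rate in 300 patients (Section 8.3). The Wald half-width is 1.96 × √(0.10 × 0.90 / 300) = 3.39%, which agrees to within about 0.1 percentage point. It has no bearing on this point.

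**Reading the sections together.** Take a patient held for more than 14 days for toxicity, without progression.

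1. Section 6.1.1 takes the patient off study.
2. Section 5.3 and the schedule plan nothing after the final visit.
3. Adverse events and unrelated serious adverse events are collected to 60 days after the last dose, and related serious events without limit (Sections 7.2.1 and 7.2.2).
4. Death due to progression is not reported as a serious event. Appendix 3 sends it to the efficacy evaluation, for which no post-treatment contact is scheduled.
5. What remains is mainly deaths more than 60 days after the last dose. Only the synopsis sentence covers these.

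**Size, by illustration.** Inputs:

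- 30 treated patients (Section 3.2).
- Median PFS 12.5 months, the first-line erlotinib figure in the Section 1.2 pooled analysis. Exponential form is assumed, so λ = ln 2 / 12.5 = 0.0555 per month.
- Share q stopping before a PFS event: not in the documents; assumed 5%, 10% or 20%, which is 1.5, 3 or 6 of 30. Stops occur at a constant rate μ = λq/(1−q).
- PFS hazard after stopping is hλ, with h assumed to be 1, 2 or 3.

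If these patients are censored at the stop, the Kaplan-Meier curve estimates exp(−λt), with median 12.5 months. With complete follow-up the curve is

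S(t) = exp(−(λ+μ)t) + [μ / (λ+μ−hλ)] × [exp(−hλt) − exp(−(λ+μ)t)].

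For q = 20% and h = 3, μ = 0.25λ and the multiplier is 0.25/(1.25 − 3) = −0.143. At t = 11.3 months, λt = 0.627, exp(−1.25 × 0.627) = 0.457 and exp(−3 × 0.627) = 0.153. So S = 1.143 × 0.457 − 0.143 × 0.153 = 0.500, and the median is 11.3 months.

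Solving S(t) = 0.5 for each case:

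| Share stopping | Median, h = 1 | Median, h = 2 | Median, h = 3 | Overstatement (h = 1, 2, 3), months |
|---|---|---|---|---|
| 5% | 12.5 | 12.3 | 12.2 | 0, 0.2, 0.3 |
| 10% | 12.5 | 12.1 | 11.9 | 0, 0.4, 0.6 |
| 20% | 12.5 | 11.7 | 11.3 | 0, 0.8, 1.2 |

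**What the table covers.** It treats every later PFS event in these patients, progression as well as death, as lost, and it ignores the 60-day capture. On both counts it overstates the effect of missed deaths alone. Against that, stops concentrated early in treatment would raise the upper end, and a lower hazard after stopping would reverse the sign.

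**Interaction with the censoring rule.** No scans are scheduled after a toxicity stop, and censoring is at last contact. If survival calls are simply added, a patient who is alive but unscanned is credited with progression-free time up to each call, and a death after undetected progression is dated at the death. Both push PFS upward. The remedy therefore has to address the censoring date.

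**The case against.** The strongest reply is that the synopsis is part of the protocol and its sentence covers all living patients off drug, including those stopped for toxicity. Other provisions help. Section 4.4 mentions a post-treatment assessment at least 60 days after the final dose. Section 4.5 has patients who refuse treatment asked about further contact, and has the investigator trace those lost to follow-up. Sections 7.2.1 and 7.2.2 collect events to 60 days. Appendix 1 urges efforts to document progression after treatment ends. All of this stands. It confines the gap mainly to later deaths and makes it a failure of the body to implement a commitment already made.

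Several stronger readings are tempting but not supported:

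- *The protocol has no means of observing these deaths.* The provisions above contradict this.
- *All toxicity patients leave the study.* The off-study wording covers interruptions over 14 days or failure to recover; the most severe grades in Table 2 say only that treatment is discontinued. Section 3.1.3 defines when the treatment phase and the trial close, not when an individual leaves follow-up.
- *The survival data would go unused.* A death without progression enters PFS under Section 8.1.1. Only survival after progression has no planned analysis.
- *Overall survival must be an endpoint because Section 1.1.1 says "the main goal is to achieve symptom control and prolong overall survival".* That is disease background. The objectives in Section 2 do not include survival.
- *A definite share of PFS events will be lost.* The documents give neither a stopping rate nor a death rate after stopping, so no such count can be derived.

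It is also fair to say that the bias is small beside sampling error. With 24-month uniform accrual, a 36-month cut-off and no early stops, the expected PFS events are 30 × [1 − (0.514 − 0.136)/(24 × 0.0555)] = 21.5. An approximate 95% interval around 12.5 months is 12.5 × exp(±1.96/√21.5), or 8.2 to 19.1 months. This limits the importance of the point but does not remove the contradiction.

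**Conclusion.** The point holds as an inconsistency between the synopsis and the body that touches the primary endpoint. Deaths after a stop without progression, mainly those beyond 60 days from the last dose, can be missed, and the affected patients may be informatively censored.

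On the assumptions shown, the overstatement of median PFS runs from nothing, if hazard is unchanged after stopping, to about 1.2 months, if 20% stop and hazard triples. The stopping share, the change in hazard and the constant timing of stops are all assumptions, so the range illustrates the effect and does not predict it. The importance is low. The correction is still worth making because it is cheap and the synopsis already commits the trial to collecting the data.

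**What to change.** 1. Reconcile the synopsis End of Study entry with Sections 3.1.3, 5.3 and 6.1.1 and the Schedule of Assessments, so that stopping study treatment does not by itself end follow-up. Leave the toxicity stopping rules untouched.
2. Add a survival-status row to the schedule, from discontinuation to study end, for patients who have not refused further contact.
3. In Section 8.1.1, count deaths without progression from that source as PFS events. Censor patients without an event at their last tumor assessment, and state that a survival contact without a scan does not extend progression-free time. Say in advance how a death after a long unscanned gap is handled.
4. Optionally, add to Section 8.1.2 a descriptive Kaplan-Meier summary of the survival data that the synopsis already collects.

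The cost is some wording, one schedule row and, if the option is taken, one table. Survival data from about 30 patients will be immature and affected by later therapy, so they support description only. Patients who refuse contact will still be lost, and survival contacts do not replace the scans that would detect progression after a stop.
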